Preliminary studies with three healthy test subjects showed statistical data that indicated that the minimum number of subjects for this study is 18.⁴ We powered the t-test between pre-treatment and post-treatment data. We calculated an effect size of 0.68 for step length difference, resulting in an estimated sample size of 18 subjects. The preliminary test with healthy subjects was approved under the Einstein Healthcare Network IRB HN4365, and other preliminary tests with healthy subjects were conducted under USF IRB Pro00001858.

We have no reason to think that women and men will differ in their abilities on any of these tasks. As such, we expect to enroll approximately the same number of men and women.

5. Inclusion and exclusion criteria

We will recruit individuals with stroke for this study. If eligible and willing, individuals that participated in our previous home study may be allowed continued participation. Since the focus of this project is to ultimately use this device to help stroke survivors, we will recruit both young adults and older adults.

Inclusion criteria includes:

- 1) Age 21-80
- 2) One or more cerebral strokes, but all strokes on same side
- 3) Stroke occurred at least 6 months prior to enrollment
- 4) Gait asymmetry, but able to walk independently with or without a cane
- 5) Not currently receiving physical therapy
- 6) No evidence of severe cognitive impairment that would interfere with understanding the instructions
- 7) No evidence of one-sided neglect, affecting ambulation
- 8) At least 25 feet of walking space (does not need to be a straight line)
- 9) Weight does not exceed 275lbs

Exclusion criteria includes:

- 1) Uncontrolled seizures
- 2) Metal implants (stents, clips, pacemaker)
- 3) Pregnancy
- 4) History of a neurological disorder other than stroke (Parkinson's, MS)
- 5) Chronic Obstructive Pulmonary Disease
- 6) Uncontrolled blood pressure
- 7) Head injury in the past 90 days
- 8) Myocardial infarction within the last 180 days
- 9) Cannot rely on a rolling walker for ambulation
- 10) Severe Ataxia
- 11) Previously diagnosed vestibular ear issues

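### Exclusion 9 on rolling walkers is worded as a requirement but listed as an exclusion, so read literally it conflicts with inclusion 4

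*Combined protocol and SAP*

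**What the plan says.** Section 5 (Inclusion and exclusion criteria) gives two numbered lists. The second opens with "Exclusion criteria includes", and its ninth item is "Cannot rely on a rolling walker for ambulation".

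In the first list, inclusion 4 is "Gait asymmetry, but able to walk independently with or without a cane". It mentions a cane and no other walking aid.

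The paragraph after the lists qualifies only the ataxia and vestibular exclusions (items 10 and 11). Section 7 (Potential risks to the subjects) says that physical therapists screen for suitability and that anyone a clinician judges unsafe on the device may not start or continue. No other place in the document mentions a walker.

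**The concern.** An item under an exclusion heading is a reason to keep someone out. Item 9 is a negative statement, so its effect under that heading is the reverse of what the same words would mean as a requirement. The reader must choose between following the heading and following the apparent sense of the line.

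This is an operative rule, and many people may have to apply it. Section 3 allows medical screening by a study physician, a nurse practitioner, a rehabilitation clinician or the subject's own physician. Section 7 adds physical therapists, section 6 lists four recruitment areas, and section 9a has potential subjects look over the eligibility criteria themselves. A line that works only when read against its heading may be applied differently by different readers.

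Walking aid is also relevant to what is studied. Section 7 names falling as a risk, section 2 makes safety under caregiver supervision an objective, and section 3 allows sessions without a therapist present. The report should be able to say plainly who was eligible by walking aid.

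**Working it through.** No arithmetic applies, and the plan gives no figure to reproduce. The check compares the wording of the criteria.

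**Step 1: polarity within each list.** The exclusion list has eleven items. Ten name a condition that excludes if present, for example "Uncontrolled seizures". Item 9 is the only one phrased as a negative. The inclusion list has nine items, and four of them (5, 6, 7 and 9) are negatively phrased requirements, for example "Not currently receiving physical therapy". Item 9 of the exclusions therefore has the form of an inclusion item.

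**Step 2: literal meaning.** With the heading applied, the rule is: exclude a person if that person cannot rely on a rolling walker. The verb matters. Being unable to rely on a walker differs from not relying on one.

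**Step 3: apply both criteria to four kinds of candidate.** The last column shows what item 9 would do if read as a condition that participants must satisfy.

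| Candidate | Inclusion 4 | Exclusion 9, literal | Item 9 as a requirement |
|---|---|---|---|
| A. Walks independently, with a cane or no aid; does not rely on a walker but could use one | met | not caught | satisfied |
| B. Walks independently, with a cane or no aid; could not use a walker | met | **caught** | satisfied |
| C. Can walk independently with a cane, but relies on a walker for some walking | arguably met | not caught | **not satisfied** |
| D. Can walk only with a walker | not met, if inclusion 4 means at most a cane | not caught | **not satisfied** |

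- A is eligible on either reading.
- B is where the criteria collide: inclusion 4 admits this person and the literal exclusion rejects them.
- C is where the reading of item 9 decides eligibility, because inclusion 4 does not say whether using a walker at other times matters.
- D is not excluded by item 9 as written, but inclusion 4, read as a limit of a cane, keeps this person out.

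**Step 4: look for text that settles it.** The note after the lists covers items 10 and 11 only. Section 7 gives a general safety judgement without mentioning walking aids. Nothing corrects or explains item 9.

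**Size.** The documents give no figures on walking-aid use in the target population, so the numbers in B and C cannot be estimated. The claim is that the rule gives wrong or divergent answers for B, C and D, not that a stated share of participants is affected.

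**The case against.** The strongest reply is that the intended meaning is easy to recover. Beside inclusion 4, the line looks like a requirement placed in the wrong list, and most clinicians would probably read it that way. If all screeners do so, nobody is misclassified. The documents include no screening form, so it is unknown whether the wording is carried into one. This stands as a reason to treat the point as a drafting error. It does not make the text correct, and under that reading the line still decides candidates such as C, so it is not merely a repeat of inclusion 4.

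Two stronger readings are tempting, and the documents support neither.

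- **That the two criteria together leave almost nobody eligible.** A reader might infer this by taking the line to exclude everyone who does not rely on a walker. The text says cannot. A cane user who could use a walker (A) is not caught, and the documents do not say how large that group is.
- **That walker-dependent people would be admitted and the safety result changed.** Failing to be excluded by item 9 admits no one, since every inclusion criterion must also be met. Inclusion 4 largely blocks such candidates, and the therapist screen in section 7 is a further check. The documents give no data on fall risk by walking aid. What remains is that these are partial backstops: inclusion 4 does not name walkers, and the section 7 screen rests on judgement.

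**Conclusion.** The point holds as an error of wording in an operative eligibility criterion. As written, exclusion 9 rejects people who are unable to rely on a rolling walker, including some who meet inclusion 4, and does not exclude people who do rely on one. No other text resolves the conflict.

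Its size is limited. The sample size in section 4 and the analysis in section 3 do not depend on it, and no endpoint, estimate or test changes. The practical risk is inconsistent screening and an eligible population that cannot be described exactly by walking aid. How often that would happen cannot be derived from the documents.

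The conclusion assumes that the heading governs every item beneath it and that cannot is given its ordinary meaning of unable. Which walking-aid rule the study intends is for the sponsor to state; this review takes no position on it.

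**What to change.** The sponsor should reconcile exclusion 9 with inclusion 4 so that both point the same way, and state the intended walking-aid rule once.

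- If reliance on a walker is meant to bar entry, either move the line to the inclusion list as a requirement or keep it as an exclusion and remove the negative.
- If something else is meant, say so directly and adjust inclusion 4 to match.
- In either case, say how to treat a person who can walk with a cane but uses a walker for some walking, since neither criterion now answers that.

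Use the same wording in any screening form and in the consent materials that potential subjects see. If anyone has already been screened, check how the line was applied to them.

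The cost is about one line in the protocol and the matching line in any derived form. Nothing in the sample size or the analysis needs to change.

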During the treatment, the licensed physical therapist will determine, based on eligibility, if the participant can use the device with their caregiver providing supervision (without the presence of the physical therapist each session). To promote continued safety, the caregiver would be required to participate in a treatment session on the device and would need to demonstrate adequate knowledge of device usage as well as how to walk with the participant safely. The therapist would have weekly or monthly follow-up visits to monitor continued safety, protocol adherence, and progress. Additionally, the participant may communicate some or all sessions with a licensed therapist via telemedicine video conferencing using the 9zest digital health rehab platform (<https://9zest.com>). This communication may be used to enhance communication with the physical therapist. This telemedicine modality is verified HIPPA compliant.

A cross over component may also be employed, in which an equal number of treatment sessions will be duplicated without the device, before or after the device treatment. In a study of this type, the patients will have an equal number of sessions of treatment without the device, in the setting and in the way the treatment will occur with the device. (e.g. at home with caregiver supervision and a physical therapist intermittently following-up).

The treatment sessions will consist of approximately 30 minutes of treatment on the device. The treatment duration will be divided into up to six shorter bouts of walking to allow rest breaks between walking sessions, if needed. Additional breaks will be given as needed upon subject request. Based on the pre-treatment gait analysis, we will evaluate all parameters (such as walking speed, double limb support, stance time, etc) and make a decision to maximize their recovery in regard to which foot the device will be placed on. The device will encourage them to take larger steps with that foot. The total treatment sessions will be no longer than one hour.

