The risks for this study are slightly higher than regular walking over ground and include the possibility of falling. The risk can be compared to walking on high-heeled shoes. To minimize this risk, subjects will be screened for appropriateness of trial participation by licensed physical therapists. For subjects who may be permitted to use this device with caregiver supervision, thorough training of all caregivers will be performed and in-person or video conferencing follow-up by the physical therapist will occur as deemed necessary by the therapist. Subjects determined unable to walk safely on the device by any clinician using the device under these conditions or any reason at any time will not be allowed to continue or start the study. As such, the combined risks associated with this study are minimal.

For this home-based study, steps are taken to ensure safety. We will use a licensed physical therapist to train all caregivers to provide the appropriate level of assistance the patient needs to safely ambulate. If the patient is not able to ambulate safely on the device with caregiver supervision or the caregiver does not demonstrate the ability to safely supervise, the subject will not be allowed participation in the study. The subject will be able to call the physical therapist to discuss their progress and/or any concerns throughout the home-based treatment, at any time. To ensure a proper safety evaluation and assessment of one's home environment, the participant and their caregiver, as well as the physical therapist, must acknowledge the following within their home: proper lighting, safe hallway entrances, and removal of throw rugs and cords. Patient and caregiver will receive fall prevention education including education on the risk of falling, certain safety issues (see above), and mobility restriction. For example, the device is not to be used on stairs. In addition to fall prevention, education will be provided on movement patterns and position changes. The safety provisions will be discussed and assessed prior to the start of treatment by a licensed physical therapist.

8. The potential benefits to subjects

There is potential for subjects to improve their gait patterns, gait speed, and balance which is our hypothesis regarding this method. It may not change their gait, so there may be no benefit to subjects.

9. Human subject considerations

a. Description of the informed consent process

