The signed paper consent forms will be kept confidential and stored in a secured location. Any soft data collected will be stored in the subject's electronic record, stored in Tresorit, a fully HIPPA compliant cloud storage system, with password protection, double encryption, and limited access to only necessary personnel who are under confidentiality agreements and understand HIPPA requirements. Telemedicine modalities that may be used (9zest) are fully HIPPA compliant. The data will be anonymized and combined with data from other experiments, so the data will not be identifiable throughout the study and in all reports generated from this data.

d. Compensation

Subjects may be paid for this study. Please refer to informed consent for more detail. They will be paid within 30 days of the end of their participation in the study.

e. Withdraw from the research study

We will discontinue testing if the subject reports or we observe signs of discomfort or fatigue that interfere with their participation in the study. In any of these circumstances, the participation will immediately stop and the subject will be compensated for his/her time. Please note that the likelihood of participants experiencing these symptoms during the experiment is not greater than in their everyday lives (e.g. during walking). Since we are performing repeated-measures statistical tests, it is essential to obtain all measures from each subject. Therefore, if a subject is unable to complete the experiment, we will remove the data from analysis. Also, if a subject requests that his/her data be withdrawn, we will delete it all electronic files from our records and destroy any paper records.

10. Data and safety monitoring plan.

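### Rest breaks (section 3) and the stop for interfering fatigue or discomfort (section 9e) have no defined boundary or scope, and on the natural reading poor tolerators leave both the study and the analysis

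*Combined protocol and SAP*

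**What the plan says.** Section 3 (study design) sets about 30 minutes of walking on the device per session. It adds: "The treatment duration will be divided into up to six shorter bouts of walking to allow rest breaks between walking sessions, if needed". It then says: "Additional breaks will be given as needed upon subject request". No cause or limit is attached to those breaks. The course is at least twelve sessions over at least four weeks. Gait is evaluated beforehand and periodically during treatment, with follow-up from one week to twelve months after the last treatment session.

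Section 9e (Withdraw from the research study) gives the stopping rule: "We will discontinue testing if the subject reports or we observe signs of discomfort or fatigue that interfere with their participation in the study". The consequence follows: "In any of these circumstances, the participation will immediately stop and the subject will be compensated for his/her time". The same paragraph explains that the repeated-measures tests need every measure from each subject, and concludes: "Therefore, if a subject is unable to complete the experiment, we will remove the data from analysis".

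Section 4 (Sample size) gives 18 subjects for a pre/post t-test at an effect size of 0.68, with no allowance for dropout.

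**The concern.** Fatigue is a foreseeable event here, because section 3 builds rest into every session. The stopping paragraph reads as if written for a single-visit experiment, where ending the test and ending participation are the same thing. In a course of twelve or more sessions with a year of follow-up they are different, and the text does not separate them.

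Two things are at stake. First, a therapist or a supervising caregiver has no written basis for deciding when a tired participant takes a break and when participation ends. Second, if the stop means leaving the study, the people lost are those for whom the device was hard to tolerate. The stated goals are efficacy, safety and feasibility, and for the last two these participants are among the most informative. Removing what was already collected from them makes the loss selective as well as incomplete.

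**Working it through.** **1. The two rules side by side**

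| Question | Section 3 | Section 9e |
|---|---|---|
| Trigger | Need for rest, or subject's request | Discomfort or fatigue, reported or observed, that interferes with participation |
| Threshold | None stated | *Interfere* is not defined |
| Consequence | A break, then walking continues | Participation stops at once |
| What ends | A bout | Not stated |
| Later evaluations | Timed from the final treatment session; early stoppers not mentioned | Not mentioned |
| Data already collected | Not mentioned | Removed if the subject does not finish |

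**2. Which scope the wording favours**

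Four features point to study exit. The rule sits under a heading about withdrawing from the research. It pairs the stop with compensation, and section 9d pays subjects once their participation in the study has ended. The text that follows deals with subjects who do not finish and with requests to delete data. Section 7 (Potential risks) likewise bars people who cannot walk safely on the device from the study, with no category for stopping the device alone. In the other direction, 9e opens by speaking of discontinuing testing, which could mean one session. Study exit is therefore the natural reading, but it is not stated outright.

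**3. What removal does to the estimate**

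Let *p* be the share removed, and let μC and μS be the mean pre/post changes in completers and in stoppers. Then

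completer mean − mean in everyone = μC − [(1 − p)μC + pμS] = p(μC − μS).

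The distortion is zero only if nobody stops or if stoppers change as much as completers. Fatigue is plausibly related to walking ability, so equality cannot be assumed. With 2 of 18 removed, p = 0.11; with 4 of 18, p = 0.22. The shift is then 11% or 22% of the difference between the groups. The counts are assumptions.

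**4. What removal does to power**

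The plan's own figure comes first. For a paired t-test, n ≈ ((z₁₋α/₂ + z_power)/d)². With d = 0.68, two-sided alpha 0.05 and 80% power (neither alpha nor power is stated in section 4):

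((1.960 + 0.842)/0.68)² = 16.97, so n = 17; the exact noncentral-t answer is 19. The stated 18 lies between them.

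Exact two-sided power if d stays at 0.68:

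| Completers | Power |
|---|---|
| 18 | 77.6% |
| 17 | 74.9% |
| 16 | 72.0% |
| 15 | 68.8% |
| 14 | 65.3% |
| 12 | 57.5% |

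To finish with 18, enrolment would be 18/0.90 = 20 at 10% loss, 18/0.80 = 22.5 → 23 at 20%, and 18/0.70 = 25.7 → 26 at 30%. These loss rates are assumptions; the documents give none.

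**The case against.** The strongest reply is that the two sections are graded steps. Ordinary tiredness brings a break, and only fatigue that still interferes brings a stop. That reading is open, so a flat contradiction is not shown. It leaves the boundary undefined, however, and does not say what the stop ends.

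Four stronger readings are tempting, and the documents do not carry them.

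- **Any fatigue ends participation.** The trigger in 9e is limited to symptoms that interfere.
- **Later measurement is ruled out.** No text forbids evaluating someone who has stopped. The plan is silent, and loss of follow-up is what the natural reading implies.
- **A headcount.** If interfering fatigue arose in 1% to 3% of sessions, the chance of at least one such session in twelve would be 1 − 0.99¹² = 11.4% to 1 − 0.97¹² = 30.6%, or 2.0 to 5.5 of 18. That rate has no source in the documents. The formula also assumes independent sessions and one common rate; clustering in less fit participants would lower the count. It further assumes that every such session means study exit. The importance of the point does not rest on it.
- **Section 7 contradicts 9e.** Section 7 says: "The risks for this study are slightly higher than regular walking over ground and include the possibility of falling". Section 9e says: "Please note that the likelihood of participants experiencing these symptoms during the experiment is not greater than in their everyday lives". The first is about overall risk, with falling the only hazard it names; the second is about discomfort and fatigue. Both can be true.

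It is also fair to say that inconsistent practice across the four recruitment areas is possible rather than established, since named staff oversee and train new study staff. And section 3 already times follow-up from the last treatment session, so part of the remedy only needs to be extended to early stoppers.

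**Conclusion.** The point stands as a gap in definition with an analytic consequence. The plan does not say where a break ends and a stop begins, or what level of involvement the stop ends. On the natural reading the participant leaves the study, and 9e explicitly removes the data of non-completers. The gait results would then describe people who tolerated the device. The removal sentence does not exempt safety or feasibility data, so those results are exposed too.

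The direction of any bias in the gait results is probably favourable to the device, on the assumption that those who stop for fatigue improve less than those who finish. Its size cannot be derived, because the documents give neither a fatigue rate nor outcomes after stopping. The power figures assume two-sided alpha of 0.05 and an unchanged effect size, and show only that 18 leaves no margin for removals. The change should be made; it does not call the design itself into question.

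**What to change.** 1. Reconcile sections 3 and 9e by stating separately what ends a bout, a session, device treatment and study participation. Which symptoms trigger which step is for the sponsor's clinicians. Confine the immediate-stop sentence to the level they intend.
2. State that a participant who stops device treatment is still asked to attend the remaining scheduled gait and safety evaluations, timed from the last device session, unless consent is withdrawn.
3. Record the date and reason for every stop, at each level.
4. Replace the data-removal sentence so that the available data of early stoppers are kept. A mixed model for repeated measures, for example, uses every observed visit and does not need complete records, which answers the reason 9e gives for removal. It assumes that missing values are predictable from those observed, so the reasons for stopping should be reported alongside it. Without this step, item 2 would bring early stoppers back to visits whose results could still be excluded.

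The cost is a wording amendment to the protocol and the analysis text. The visits are already in the schedule. The average result may be less favourable once early stoppers are included.

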The goal of this study is to test the efficacy, safety, and feasibility of the iStride™ device to correct gait asymmetry and improve gait parameters including gait speed and balance in individuals with stroke. The study will be structured around subjects walking on the device with their gait recorded and analyzed before and after device usage. The study design is within-subjects where each individual's gait will be compared before, during, and after the treatment period. The study will be conducted on chronic stroke patients in a home-based setting. The treatment will last at least four weeks with an initial visit prior to the start of treatment and several follow-up tests targeted at one month, three months, six months and twelve months post-treatment, in order to measure retention. A subset of the home study patients may be asked to continue treatment with variations in frequency and duration. In addition, several customization factors, specifically to the wheel size, may be tested in order to determine if patients plateau at any point during their rehabilitation. This is important in order to determine the most beneficial prescription for patients while using the device. Additionally, in order to assess muscle activation and response, a subset of these subjects may be asked to visit an alternate clinic site for EMG testing pre and post-treatment.

The home-based treatment will consist of at least twelve treatment sessions performed over a minimum of four weeks with a gait evaluation pretest and initial fitting of the shoe the week before. Gait evaluations will be performed the week before the first treatment and periodically during treatment (no more than once per week). Follow-up tests will be targeted at one week, one, three, six, and twelve months after the final treatment session.

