A study physician or an advanced registered nurse practitioner (ARNP), rehabilitation clinician with knowledge, or subject's physician will perform medical screening or sufficient review of a medical record for the subjects that will participate in the proposed studies. This screen will be used to determine if the potential subjects had one or more cerebral strokes without other medical conditions (e.g., other neurological, orthopedic, etc.) that would affect or explain the subjects' walking or limb movement. Clinical assessments may consist of vision, proprioception, gait analysis and cognitive screening. The 10 Meter Walk Test, Timed Up and Go Test²⁴, Berg Balance Scale, and Functional Gait Assessment tests will be performed to assess changes in subjects' gait velocity, aerobic capacity, and risk of falls, respectively, before, during, and following treatment. Additionally, several psychosocial outcomes will be tested.

To measure gait, Veristride motion sensors will be incorporated. These sensors, along with additional sensors will be used during all treatment sessions creating a complete library of data while using the device during treatment. This data will be analyzed with existing algorithms to measure gait parameters as well as assess changes that may occur as a result of iStride™ device usage. For the subjects in this study who perform treatment with caregiver supervision, these sensors will allow us to verify that the subject completed the treatment as specified. A fit bit device may also be used in this study, in order to track compliance, record telemetry-related data, as well as provide an overall collection of steps per patient.

Our main analysis will be to compare the amount of learning (i.e. deviations from symmetry post-adaptation) to normal baseline symmetry. This will be done using a repeated measures ANOVA to compare baseline gait symmetry at the start of the experiment to post-adaptation at the end of the experiment and on the follow-up assessments. We will quantify the amount of adaptation and the change in gait asymmetry by comparing the magnitude of step length and double support differences during baseline, at the beginning of treatment, during treatment, and after treatment. During a symmetric gait, step lengths on each side are the same; during an asymmetric gait, step lengths are different. These measures are standard accepted measures for measuring gait asymmetries.

4. Sample size

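### Removing every subject who does not complete an undefined experiment selects the before-after estimate on completion

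*Combined protocol and SAP*

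**What the plan says.** Section 9e (Withdraw from the research study) gives the rule, "Therefore, if a subject is unable to complete the experiment, we will remove the data from analysis", and its reason: because the tests are repeated-measures tests, "it is essential to obtain all measures from each subject". The same paragraph ends participation on "signs of discomfort or fatigue that interfere with their participation in the study". Section 7 (Potential risks to the subjects) adds "Subjects determined unable to walk safely on the device by any clinician", who may neither start nor continue, at any time.

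Section 3 describes the main analysis of gait symmetry: "This will be done using a repeated measures ANOVA", comparing baseline with "post-adaptation at the end of the experiment and on the follow-up assessments". It sets a minimum amount of treatment, "at least twelve treatment sessions performed over a minimum of four weeks", and leaves the maximum open: "A subset of the home study patients may be asked to continue treatment with variations in frequency and duration". One paragraph of section 3 starts follow-up at one month, the next at one week; both run to twelve months. A crossover period without the device is optional.

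No section defines completion, names another analysis set, or gives a missing-data method or sensitivity analysis. Section 10 says that the whole data set, all subjects, is analysed after each experiment. That sentence is about timing and does not bring removed subjects back.

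**The concern.** The design is within-subjects and the comparison period is optional, so any selection of subjects passes directly into the before-after estimate. Two of the plan's own reasons for stopping concern how well a subject tolerates the device or walks on it, and these may be related to response. A reader of the results could not tell whether the estimate describes everyone treated or only those who tolerated the device.

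Because completion is undefined, the analyst must also decide who counts, possibly after seeing data. The boundary could be the twelfth session, the end of any extended treatment, the crossover, the one-week test or the twelve-month visit.

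The stated reason does not require the rule. A classical repeated-measures ANOVA on complete cases needs every measure. A likelihood-based mixed model does not.

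**Working it through.** **The plan's own figure.** Section 4 gives an effect size of 0.68 for a pre-post t-test and 18 subjects. Alpha and power are not stated. With two-sided 0.05 and 80% power assumed, n = ((1.960 + 0.842)/0.68)² = 16.97, so 17; the exact t calculation gives 19. The stated 18 is consistent with this, though other settings also come close. No dropout allowance is stated.

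**What counts as completion.** Section 3 lists the end of the experiment apart from the follow-up assessments, which points to the end of treatment. Section 9e asks for all measures, and the ANOVA includes the follow-ups, which points to twelve months. The text does not settle it.

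**Selection on completion: general form.** Completer mean minus all-enrolled mean = dropout × (completer mean − non-completer mean). At 20% dropout and a gap of 0.5 to 1.0 SD this is 0.10 to 0.20 SD. With no gap it is zero.

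**Illustration (every input is an assumption).** Baseline asymmetry B ~ N(0,1); post-treatment P has equal variance and correlation 0.5 with B; improvement C = B − P has mean 0.50, variance 1 + 1 − 2×0.5 = 1 and covariance with B of 1 − 0.5 = 0.5. Dropout p follows a normal liability with link r, and λ = φ(z)/(1 − p): 0.4237 at p = 0.25 and 0.1950 at p = 0.10.

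- (a) Dropout follows poor change: completer mean = 0.5 + rλ.
- (b) Dropout follows baseline severity: completer mean = 0.5 − 0.5rλ.
- No improvement assigned to dropouts: (1 − p) × completer mean.
- The mixed-model row is by simulation, with all baselines and the completers' post values.

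| Estimate in SD (truth 0.50), r = 0.3 / 0.5 / 0.7 | (a) | (b) |
|---|---|---|
| Completers, 10% loss | 0.56 / 0.60 / 0.64 | 0.47 / 0.45 / 0.43 |
| Completers, 25% loss | 0.63 / 0.71 / 0.80 | 0.44 / 0.39 / 0.35 |
| Mixed model, 25% loss | 0.60 / 0.66 / 0.74 | 0.50 / 0.50 / 0.50 |
| No improvement for dropouts, 25% loss | 0.47 / 0.53 / 0.60 | 0.33 / 0.30 / 0.26 |

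In (a) the mixed model removes only part of the bias. At r = 0.5 that is (0.712 − 0.664)/0.212 = 23%; across the three links it is about a fifth to a quarter. In (b) it removes all of it when variances are equal.

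**Unequal variances in (b), 25% loss, r = 0.5.** The covariance of B and C becomes 1 − 0.5 × (post SD). With post SD 0.7, completers give 0.5 − 0.65×0.5×0.4237 = 0.36; with 1.3 they give 0.5 − 0.35×0.5×0.4237 = 0.43. A compound-symmetry model gives 0.47 and 0.54 respectively; an unstructured one gives 0.50 in both.

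**Late visits (wider reading only).** If completion includes the tests at one, three, six and twelve months, and each is missed independently with probability h, the share of valid pairs deleted is 1 − (1 − h)⁴. For h = 2%, 5% and 10% this is 7.8%, 18.5% and 34.4%, and times 18 gives 1.4, 3.3 and 6.2 subjects. For scale, exact power at 0.68 (two-sided 0.05) is 77.6% with 18 pairs, 72.0% with 16, 65.3% with 14 and 57.4% with 12.

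**The case against.** The strongest reply is that the rule is narrower than it sounds. Its only stated reason is repeated-measures testing, and the only such analysis described is the gait-symmetry ANOVA, so it probably concerns efficacy data. Section 3 places the end of the experiment before follow-up, and section 10 has data checked shortly after the experiment. Both favour end of treatment, and on that reading a missed late visit deletes nobody. Part of section 7 describes subjects who never start; they have no before-after pair and are not part of this selection. Section 9e says that the symptoms are no more likely than in everyday life. Section 1 reports 15 earlier home users with one adverse event and no stated dropouts, so the 25% loss has no anchor in the documents.

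Much of this stands. It limits the reach of the point and the late-visit figures. It does not remove the core: on the narrow reading too, a subject who starts the device and stops for discomfort, fatigue or unsafe walking is dropped, and no other analysis includes that subject.

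A reader might infer that adverse events of removed subjects will go unreported. The documents do not say so. The rule simply has no exception for safety data, and section 10, despite its title, describes no safety analysis. Since section 3 names safety and feasibility as goals, this needs a clarifying sentence, but it is not a demonstrated loss of safety data.

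**Conclusion.** The point holds for the efficacy analysis and should be fixed before data are analysed. Applied as written, the rule selects the before-after estimate on completion under either reading of completion, and its stated justification applies only to a complete-case ANOVA.

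A reader might go further and conclude that the reported benefit will be inflated. The documents do not support that. Bias is upward if those who stop improve less, downward if those who stop have the worst baseline and more room to improve, and zero if they do not differ. The illustrative range at 25% loss, 0.35 to 0.80 SD around a true 0.50, rests wholly on the assumed dropout rate, links, correlation and equal variances. The loss of 1.4 to 6.2 valid pairs of 18 rests on the wider reading and on independent missed visits.

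**What to change.** 1. **Define completion and replace the deletion rule.** Analyse every subject with a baseline and at least one device session. Use all available data at a few prespecified time points (baseline, first post-treatment test, follow-ups) in a likelihood-based mixed model with small-sample degrees of freedom, for example Kenward-Roger. Name baseline versus first post-treatment test as the main contrast and state its timing, because section 3 gives both one week and one month as the earliest follow-up. Keep completers-only as a sensitivity analysis.

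2. **Keep the covariance small and suited to the visits.** Do not use a first-order autoregressive structure by visit order, since the visits are unequally spaced. Check compound symmetry against a structure that lets variances differ by visit. With baseline, one week and one, three, six and twelve months there are six time points: compound symmetry has 2 parameters, visit-specific variances with one correlation have 6 + 1 = 7, and unstructured has 6×7/2 = 21, too many for about 18 subjects.

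3. **Add one sensitivity analysis** assigning no improvement to subjects who stopped for unsafe walking, discomfort or fatigue. The mixed model assumes missing at random and corrects little in scenario (a). The no-improvement analysis overcorrects in (b), so neither is enough alone.

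4. **Clarify** that the removal rule does not apply to safety and feasibility, which are reported for everyone who used the device. Record and tabulate the reason for each stop. Data that a subject asks to withdraw stay under the plan's separate deletion rule.

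The cost is protocol wording, slightly more analysis work, one recorded reason per stop (the documents do not say that reasons are recorded now), and a possibly less favourable estimate.
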